6.1.1 Treatment regimens / study intervals

In general, if bridging is documented in the CRF, all chronic antithrombotic treatments are stopped, therefore set "antithrombotic treatment stop date = bridging start date - 1" and "Antithrombotic treatment start date = bridging stop date + 1" prior to derivation of treatment interval. Bridging documented up until two weeks after baseline visit, will however be ignored.

Table 6.1.1: 1 Treatment regimens

Regimen label	Regimen decode	Derivation for start date
Pre-treatment	Pre-treatment	minimum of date of ICF sign off, date of baseline visit and date of any AE
Treatment	VKA VKA+ASA VKA+Clopi DE 110mg bid DE110mg bid +ASA DE150mg bid DE150mg bid +ASA ASA Clopi Clopi+ASA ...<all other mono-therapies and actual observed combination therapies> None	For each day from minimum of date of ICF sign off, date of baseline visit and date of any AE, determine treatment status of patient. Combine consecutive days with same regimen decode to treatment interval.
Washout	Washout	Drug stop date +1 day, if the previous treatment was a single treatment or if all drugs administered as combined therapy are stopped simultaneously (i.e. same stop date); duration of washout is 3 days for treatments other than VKA and 6 days for VKA.
Post-study	Post-study	date of study completion/discontinuation +1 day

6.1.2 Specification of treatments for analyses

Reference time periods for the analysis of outcome events, exposure time, AEs are specified in the study protocol:

A patient is considered to have permanently stopped initial antithrombotic treatment according to the definition of antithrombotic treatment start and stop date provided in [Table 6.1.2:1](#).

For the main analysis (as treated analysis) of outcome events, patients will be grouped according to the therapy prescribed for long term treatment at baseline visit, excluding patients who never took the prescribed medication. This will be derived based on the CRF question on planned long-term AF treatment documented at baseline. The number and percentage of patients who never took the prescribed medication (defined as not taken one single dose of prescribed medication) will explicitly be shown in the disposition table (see [Table 6.4:1](#)); they will be excluded from all main outcome analyses if they did not take the treatment group defining medication (e.g. a patient prescribed to VKA+Clopidogrel which took only VKA will be grouped as a VKA patient; a patient prescribed to VKA+Clopidogrel and took only Clopidogrel will be excluded from all main outcome analyses). For potential outcome analyses patients will be included under the treatment (mono/combi) and dose they

were prescribed and actually took. Start and end of initial treatment regimen episode which will be used as analysis period for the main analysis of outcome events are defined as follows:

Table 6.1.2: 1 Treatment regimen episode start and stop

Treatment group	initial treatment regimen episode start	initial treatment regimen episode stop
(Combinations with) NOAC_X* - excluding combinations with other (N)OACS:	
The NOAC treatment start date starts active medication;
 
 if NOAC treatment start date < min(date of ICF sign off, date of baseline visit) then use min(date of ICF sign off, date of baseline visit) instead if NOAC start date is missing then use date of ICF sign-off. 	minimum{ 
 permanent stop\$ date of NOAC+3days, start date of other chronic anticoagulant treatment (i.e. VKA, new oral anticoagulants other than original NOAC) -1day date of study completion/discontinuation }
Combinations of NOAC_X* and oral anticoagulant(s)	
 The FIRST NOAC treatment start date starts active medication; if NOAC treatment start date < min(date of ICF sign off, date of baseline visit) then use min(date of ICF sign off, date of baseline visit) instead if NOAC start date is missing then use date of ICF sign-off. 	minimum{ 
 permanent stop\$ date of NOAC+3days, last permanent stop date of oral anticoagulant (other than NOAC) + 6 days (for VKA), + 3 days (for oral anticoagulant other than VKA) date of study completion/discontinuation }
(Combinations with) VKA - excluding NOACs:	
 The VKA treatment start date starts active medication; if VKA treatment start date < min(date of ICF sign off, date of baseline visit) then use min(date of ICF sign off, date of baseline visit) instead if VKA start date is missing then use date of ICF sign-off. 	minimum{ 
 permanent stop\$ of VKA+6days), start date of other chronic anticoagulant treatment (i.e. dabigatran, other new oral anticoagulants) -1day date of study completion/discontinuation }
(Combinations with) ASA - excluding VKA, NOACs:	
 The ASA treatment start date starts active medication; if ASA treatment start date < min(date of ICF sign off, date of baseline visit) then use min(date of ICF sign off, date of baseline visit) instead if ASA start date is missing then use date of ICF sign-off. 	minimum{ 
 permanent stop\$ of ASA+3days, start date of other chronic antithrombotic treatment (i.e. VKA, new oral anticoagulants)-1day, date of study completion/discontinuation }
(Combinations of) Antiplatelets other than ASA	
 The first antiplatelets treatment start date starts active medication; if first antiplatelets treatment start date(treatment start date < min(date of ICF sign off, date of baseline visit) then use min(date of ICF sign off, date of baseline visit) instead if first antiplatelets treatment start date(start date is missing then use date of ICF sign-off 	minimum{ 
 permanent stop\$ of all {Antiplatelets other than ASA}+3days, start date of other chronic antithrombotic treatment (i.e. ASA, VKA, new oral anticoagulants)-1day, date of study completion/discontinuation}
None	
 Baseline visit date is start date 	minimum of { 
 start date of chronic antithrombotic treatment)-1day, date of study completion/discontinuation }

\$Treatment interruptions (due to bridging or for any other reasons) of more than 30 days are considered permanent stop of medication. Shorter treatment interruptions will be disregarded for the analysis of outcome events (i.e. patient is considered to be on continuous treatment).

*for new oral coagulants/non-VKA oral coagulants (NOACs) in general separate treatment groups for Dabigatran, Rivaroxaban, Apixaban and Edoxaban will be presented. NOAC_X stands for one specific NOAC out of the following: Dabigatran, Rivaroxaban, Apixaban, or Edoxaban

For the sensitivity analysis of outcome events according to the intention-to-treat approach (analysis by carrying forward antithrombotic treatment at baseline), patients will not be censored after index treatment discontinuation (for additional details, see [Section 6.8](#); in particular, an exception is the event death, i.e. death captured via the vital status page will still be considered after the patient's discontinuation). This analysis is based on the same patient set as the main analysis (i.e. the "restricted" and "matched" patient sets, only including those who took at least once the treatment, see [Section 6.3](#)). Study period refers to the time from start of initial treatment regimen (see [table above](#)) to start of the post-study phase (see [Table 6.1.1:1](#) in [Section 6.1.1](#)).

Furthermore (1160.129 only), regarding baseline data and incidence rate analyses, the cohort of patients initiating (Combinations with) DE – excluding combinations with other (N)OACs (this group is part of first definition shown in [Table 6.1.2:1](#)), at baseline will be further stratified by Dabigatran mono vs combi-therapy and by dose. Additionally, the outputs by dose will be broken down by US and Non-US patients (as the 75mg dose is only approved for SPAF in US). The analyses regarding baseline data will be performed for the categories with at least 100 patients at baseline. The analyses regarding incidence rates will be performed at least for the main composite outcome for the categories with at least 500 patients at baseline. Analysis periods for analyses of outcome events are defined as follows:

Table 6.1.2: 2 Treatment regimen episode start and stop (mono/combi therapy and by dose)

Treatment group	initial treatment regimen episode start	initial treatment regimen episode stop
Mono/Combi Therapy		
DE mono-therapy	
The DE treatment start date starts active medication;
 
 • if DE treatment start date<min(date of ICF sign off, date of baseline visit) then use min(date of ICF sign off, date of baseline visit) instead • if DE start date is missing then use date of ICF sign-off. 	minimum{ 
 • permanent stop⁺ date of DE+3days, • start date of other chronic anticoagulant treatment or antiplatelet treatment - 1day • date of study completion/discontinuation }
DE combi-therapy	
The DE treatment start date starts active medication;
 
 • if DE treatment start date<min(date of ICF sign off, date of baseline visit) then use min(date of ICF sign off, date of baseline visit) instead • if DE start date is missing then use date of ICF sign-off. 	minimum{ 
 • permanent stop⁺ date of DE+3days , • permanent stop⁺ date of any of the combi antithromb. therapies administered +3days , • start date of other chronic anticoagulant treatment -1day • date of study completion/discontinuation }
Analysis by dose		
DE 110mg bid	
The DE treatment start date starts active medication;
 
 • if DE treatment start date<min(date of ICF sign off, date of baseline visit) then use min(date of ICF sign off, date of baseline visit) instead if DE start date is missing then use date of ICF sign-off. 	minimum{ 
 • permanent stop⁺ date of DE+3days, • change in DE dose – 1 day • start of other chronic anticoagulant treatment -1day • date of study completion/discontinuation }
DE 150mg bid	
The DE treatment start date starts active medication;
 
 • if DE treatment start date<min(date of ICF sign off, date of baseline visit) then use min(date of ICF sign off, date of baseline visit) instead if DE start date is missing then use date of ICF sign-off. 	minimum{ 
 • permanent stop⁺ date of DE+3days, • change in DE dose – 1 day • start of other chronic anticoagulant treatment -1day • date of study completion/discontinuation }
DE 75mg BID	
The DE treatment start date starts active medication;
 
 • if DE treatment start date<min(date of ICF sign off, date of baseline visit) then use min(date of ICF sign off, date of baseline visit) instead if DE start date is missing then use date of ICF sign-off. 	minimum{ 
 • permanent stop⁺ date of DE+3days , • change in DE dose – 1 day • start of other chronic anticoagulant treatment -1day • date of study completion/discontinuation }

For the analysis of adverse events, the concept of treatment emergent AEs will be used, i.e. an AE is assigned to the treatment group under which it occurred whereas AEs with onset time during the washout period are to be assigned to the previous active treatment.

Note: not all active treatment intervals are followed by a washout period (“switcher”; as defined in [Section 7.7](#), patients are considered switchers if they initiate another OAC within 30 days after stop of index treatment); the term “treatment period” refers to the time period of active treatment interval including the consecutive washout period (if applicable). The length of washout, 3 days for NOACs and 6 days for VKA, is defined based on pharmacologic

properties of the treatments (half-life of the drug). Further sensitivity analyses with a different washout period length or a different definition of “permanent stop of medication” might be considered.

6.2 IMPORTANT PROTOCOL VIOLATIONS

Table 6.2: 1 Important Protocol (eligibility criteria) violations

Category / Code		Description	Definition	Excluded from	To be checked manually?
A		Entrance criteria not met			
	A1	Inclusion criteria not met			
	A1.1	Age < 18 years Age <20 years for Japan only		All eligible	no
	A1.2	Informed consent not given Privacy form missing		All enrolled	No yes
	A1.3	Informed consent given too late		None	no
	A1.4	No new AF diagnosis ≥ 3 months between date of diagnosis and date of baseline visit ≥ 4.5 months between date of diagnosis and date of baseline visit for Latin American region only		All eligible	no
	A1.5	No additional risk factor		All eligible	no
	A1.6	Other deviations in terms of informed consent process		None	yes
	A2	Exclusion criteria violated			
	A2.1	Presence of any mechanical heart valve, or valve disease that is expected to require valve replacement intervention (surgical or non-surgical) during the course of the assigned registry phase.		All eligible	no
	A2.2	Warfarin prevalent		All eligible	no
	A2.3	AF with a generally reversible cause		All eligible	no
	A2.4	Life expectancy < 1 year		All eligible	no
	A2.5	Patient with medical condition other than AF for which chronic use of an oral anticoagulant (VKA) is indicated		All eligible	no
	A2.6	Participating in any clinical trial of a drug or device		All eligible	no
	A2.7	Current participation in an international registry on the use of oral anticoagulation in AF		All eligible	no

Table 6.2: 1 Important Protocol (eligibility criteria) violations (Continued)

Category / Code	Description	Definition	Excluded from	To be checked manually?
A2.8	Patient was enrolled in any other phase of the GLORIA-AF Program		All eligible	no
A2.9	Patient with no further follow-up possible with enrolling investigator during planned study period (such as anticipated relocation)		All eligible	no

According to the study protocol, patients who are erroneously enrolled, should be discontinued from study (i.e. documentation in EDC should be terminated) as soon as the violation of in-/exclusion criteria is identified. The violation of in-/exclusion criteria should be reported on the end of study form. Patients who develop a violation of in-/exclusion criteria during the course of the study but who did not violate any in-/exclusion criteria at baseline will NOT be discontinued automatically but can be withdrawn if they participate in another international drug study or registry on the use of oral anticoagulation in AF, or in a clinical trial with a drug or device. The exception is with clinical studies of idarucizumab (Praxbind) where explicit provision for collection of this data has now been included.

The important protocol violations (PVs) which result in exclusion from any analysis population ("all enrolled" or "all eligible") correspond to those in/exclusion criteria for which violation will result in discontinuation of patient from study.

The important protocol (eligibility criteria) violations will be described in the study report. A summary table of protocol violations will be created based on "all enrolled" (see [Section 6.3](#)) patients.

Based on the CRF, all important protocol violations given in [Table 6.2: 1](#) will be identified programmatically in SAS (based on the End-of-Study CRF page and for ICF based on the baseline forms) except for A1.6 which is handled as manual IPV and occurrences need to be reported to the study team by the Co-CTLs for each region during e.g. Medical and quality review meetings. Additional important PVs might be defined during the course of the study and will be assessed during the Medical and quality review meetings; if the list of important protocol violations needs to be enlarged, this will be documented in the report planning meeting minutes before database lock.

In case of important site level protocol violations additional sensitivity analyses excluding patients from those sites might be performed.

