6.2 DETAILS OF STUDY PROCEDURES AT SELECTED VISITS

6.2.1 Assessments in Phase II of GLORIA-AF

The following data will be collected for all patients in Phase II at enrollment, for the purposes of cross-sectional analyses. Follow-up assessments will be done only in patients who receive dabigatran. The baseline visit is defined as the physical visit when the patient is enrolled in the registry.

Assessments at Baseline:

- Date of baseline visit
- Date of informed consent
- Date of diagnosis of non-valvular AF
- Inclusion/exclusion criteria
- Demographic data, including: date of birth (month and year), gender, weight, height (calculated BMI) and race
- Blood pressure, heart rate and serum creatinine (if available)
- Information regarding AF
 - Symptomatic, minimally symptomatic, asymptomatic
 - Type (paroxysmal, persistent, permanent)
 - Previous cardioversion, ablation, pacemaker, implantation, use of LAA occlusion device and/or left atrial procedures
- Medical history (including current concomitant diseases)
- Selected concomitant treatments (antihypertensive, heart failure and anti-arrhythmic therapies, metabolic and anti-inflammatory) and other selected drugs.
- Antithrombotic treatment selected including start date (all antithrombotic therapies, for stroke prevention as well as other indications).

Assessments at the Follow-up Visits (cf. [Flow Chart](#)):

- Date of follow up visit
- Type of follow up visit
- Concomitant diseases (current, any change)
- Serum creatinine to be recorded (if available)
- Antithrombotic treatment (current, any change (start and stop dates) including compliance, reason for change; including interruptions of antithrombotic treatment due to therapeutic/diagnostic interventions)
- Selected concomitant treatment (current, any change)
- Outcome events as listed in [Section 5.1](#)
- Information is recorded on any therapeutic/diagnostic interventions that occur as part of regular follow-up
- All serious adverse events judged as related or unrelated to any BI drug (see [section 5.2.2.2](#))
- Non-serious adverse events judged as related to any antithrombotic therapy including dabigatran or to any BI drug (see [section 5.2.2.2](#))

Proprietary confidential information.

© 2014 Boehringer Ingelheim International GmbH or one or more of its affiliated companies. All rights reserved.

This document may not - in full or in part - be passed on, reproduced, published or otherwise used without prior written permission.

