6.8 CALCULATION OF TIME TO EVENTS OR CENSORING

The derivations of time to event and time to censoring for the time to event analyses are specified in this section. The information from the outcome event pages will be used to collect events. Deaths reported via the vital status or serious adverse event page will also be included.

Events to be counted in the study period are all events with onset date \leq patient’s study termination date. Events occurring after the patient’s study termination date will NOT be included in the analysis (irrespective of whether they occur during the washout period or later) as treatment information will in general not be documented in the CRF for this time period. The event death is an exception. Death captured via the vital status page will still be considered after the patient’s discontinuation.

For composite outcome events, the onset date of the first occurring component event will be used.

The following rules will be used for the main analysis of outcome events:

The analysis will be based on the antithrombotic treatment choice selected at baseline (long-term treatment information, as collected in the following CRF question: “Please report any antithrombotic treatments that you prescribed for long term use at the time of the baseline visit, or any antithrombotic treatments that the patient was already on at the time of the baseline visit that the patient will remain on for long term use”) and the initial treatment regimen episode (as specified in [Section 6.1.2](#)). An event will be counted for the main analysis if it occurs during the initial treatment regimen episode of the antithrombotic therapy selected at baseline.

The time to event will be calculated as: event date - initial treatment regimen episode start date + 1.

The time to censoring will be calculated as initial treatment regimen episode stop date - initial treatment regimen episode start date + 1 (as described in [Table 6.1.2:1](#)).

Patients participating in a clinical trial with a drug or device or in another international drug study or registry on the use of oral anticoagulation in AF will be censored when they enter the trial/study. The exception is with clinical studies of idarucizumab (Praxbind) where explicit provision for collection of this data has now been included.

The following rules will be used for the intention-to-treat analysis of outcome events :

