Within Phase III an interim analysis of baseline characteristics will be conducted after recruitment of e.g. at least 15,000 eligible patients in the registry is completed. Analyses on country level might be performed in addition based on the data snapshot used for these interim analyses and/or country-specific amendments.

For this interim analysis, all analyses specified for the final analysis of phase III data on demographics and baseline characteristics will be conducted as well as an overview of non-eligible patients and overall disposition.

Timing and scope of work considerations

Scheduling of IA:

The data cut-off date for this analysis will be defined by the OC at least two months prior to the actual date. The OC needs to ensure that a minimum of 15000 eligible patients are in the database for phase III at the date of data cut-off.

Description of the data needed for the IA:

The baseline CRF forms (including the eligibility page) as well as the CT CRF pages and the End-of-study information (to check for eligibility status of patients) are required for the IA.

Format of the interim report:

A brief textual summary or synoptic interim report will be used to summarize the results of the interim analysis.

Level of database clean-up and coordination of timing

The data cut-off date as defined by the OC will be approximately 8 weeks prior to the date of snapshot creation.

The interim analysis will include all eligible patients who fulfil the following criteria:

- baseline visit <= data cut-off date
- All baseline CRF pages have a completion and approval flag, CT page marked as complete
- Number of manual (monitor) queries on baseline CRF and on CT page and end of study page <5

**7.10.5 Optional interim analysis on Phase III data prior to final database lock for
Phase III to obtain preliminary results on baseline characteristics and on
follow up data of AF population (study 1160.129 only)**

Optionally, an interim analysis of cross-sectional and follow up data may include analysis of treatment and/or clinical management decisions of patients enrolled in phase III when enough follow-up data is available and reasonably complete, e.g. 1 year follow up.

The results of this interim analysis will be incorporated in the interim report of interim analyses 7.10.1 and 7.10.4 (brief textual summary or synoptic interim report).

The interim analysis will include all eligible patients who fulfil the following criteria:

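### Eligibility is read from a site-completed End-of-Study page, with no stated cross-check against baseline data and no guard against hindsight reporting of expectation-based criteria

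*SAP*

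**What the plan says.** SAP 6.2 says the violations in Table 6.2:1 are "identified programmatically in SAS (based on the End-of-Study CRF page and for ICF based on the baseline forms". Consent is thus read from baseline forms, and A1.6 is named as the manual exception. All other codes depend on the End-of-Study page.

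Entries reach that page by site report: "The violation of in-/exclusion criteria should be reported on the end of study form". On timing, documentation should stop "as soon as the violation of in-/exclusion criteria is identified", with no cut-off date.

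In Table 6.2:1, A1.1 (age), A1.4 (time since AF diagnosis), A1.5 (no risk factor) and A2.1 to A2.9 each remove the patient from the eligible set. All are marked as not needing a manual check. A1.4 is written as a date difference: "≥ 3 months between date of diagnosis and date of baseline visit", with a longer limit for Latin America.

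SAP 6.3 builds the eligible set on this table. The restricted set, which carries the main Cox comparison, is drawn from eligible patients, and the propensity scores used for matching are based on eligible patients too.

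SAP 7.10.4 lists "The baseline CRF forms (including the eligibility page" among the data for the baseline interim analysis, but names the End-of-Study information as the item used to check eligibility status.

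Protocol 6.2.1 collects "Date of diagnosis of non-valvular AF" at baseline, together with the visit date, month and year of birth, the inclusion and exclusion criteria, and medical history. Protocol 6.2.2 makes the Phase III baseline assessment identical.

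**The concern.** Two things are at stake.

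The first is enforcement of the population. Protocol 7.3 analyses patients who meet all inclusion and no exclusion criteria. Under SAP 6.2, whether that holds depends on each site noticing and reporting a failure, even where dates and risk factors already in the database would settle it.

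The second is the order of events. Three exclusion criteria are forecasts: expected valve replacement (A2.1), life expectancy under one year (A2.4) and no further follow-up possible (A2.9). A forecast recorded on an exit form may be written by someone who already knows what happened. If such an entry follows an outcome event, the exclusion removes that event from the main analysis. Treatment is known to everyone in this registry, so such entries could differ between dabigatran and VKA patients.

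**Working it through.** **Step 1. Criteria that baseline data can decide.**

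| Code | Failure | Baseline data that show it | Source named in SAP 6.2 |
|---|---|---|---|
| A1.1 | under 18 (under 20 in Japan) | month and year of birth, visit date | End-of-Study page |
| A1.4 | 3 months or more since diagnosis (4.5 in Latin America) | diagnosis date, visit date | End-of-Study page |
| A1.5 | no risk factor | age, sex, medical history | End-of-Study page |

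Take a European patient diagnosed 5 months before baseline. Since 5 ≥ 3, A1.4 is violated. If the site makes no End-of-Study entry, the stated algorithm returns no flag and the patient is eligible. After one dose, and with a propensity score inside the trimmed overlap, a dabigatran or VKA patient also enters the restricted set.

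**Step 2. Criteria that are forecasts.** Protocol 3.3.3 fixes the life-expectancy judgement at the time of potential enrolment. The label in SAP Table 6.2:1 omits that anchor. SAP 6.2 does say that patients who develop a violation later, but had none at baseline, are not discontinued automatically. The intent is therefore baseline status. What is missing is a means of verifying it. The SAP asks for no evidence that the expectation existed at enrolment, makes no comparison of report date with event date, and plans no review blind to outcome or treatment.

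Take a patient who dies at month 4 and whose exit form cites A2.4. Nothing in the stated procedure separates a genuine enrolment error from a judgement made with hindsight, and in both cases the death leaves the outcome analyses.

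**Step 3. Do the planned checks cover this?** SAP 6.3 recognises that excluding patients who differ in exposure or outcome can cause selection bias. It orders comparisons of outcomes and treatment, and of baseline characteristics if there are at least 100 such patients. These concern only patients dropped for incomplete or unapproved forms. The first sensitivity analysis there is stricter. The second removes the form criteria but still requires Table 6.2:1 to be met. Neither restores a patient excluded under Table 6.2:1.

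**Step 4. Size.** The documents give no count of violations, of exclusions or of events preceding them. A conditional illustration can start from protocol 7.6, which expects 4,019 patient-years for 2,000 patients over 3 years at 25% loss per year.

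- Check: λ = −ln(0.75) = 0.2877, and 2,000 × (1 − 0.75³)/λ = 2,000 × 0.578125/0.2877 ≈ 4,019. The protocol figure reproduces.
- At the protocol's 1 to 3 events per 100 patient-years (given for stroke/systemic embolism and for major bleeding, not for the composite), the cohort has about 40 to 121 events.
- Assume 10% of one group's event patients are excluded after the event. That is about 4 to 12 patients, or 0.2% to 0.6% of 2,000. If each contributed 0.25 to 0.75 years, the group's rate becomes 0.900 to 0.902 of its former value.
- Assume instead that a fraction f of retained patients is ineligible, with m times the event rate. The rate is multiplied by 1 − f + f·m. For f = 1% to 5% and m = 1.5 to 3 this runs from 1.005 to 1.10.

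The 10%, f, m and the follow-up times are all assumptions. The illustration shows only that few patients would be needed to move a rate by an amount similar to the 10% change-in-estimate threshold in SAP 7.6.

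**The case against.** **Other controls exist.** Protocol 8.2 provides eCRF edits for out-of-range or illogical data, possible cross-form checks and queries under a data management plan. Protocol 3.2.1 has charts reviewed by site staff and at monitoring visits. The criteria are also recorded at baseline. A reader should therefore not infer that baseline data go unchecked, and an under-age patient may well be queried. This stands, but none of these controls is tied to the eligible-set flag, and the data management plan is not among the documents.

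**The SAP counts baseline violations only.** A reader might infer that a later valve operation, relocation, death or trial entry is itself grounds for exclusion. The documents do not support that. SAP 6.2 addresses violations that develop later, and Table 6.2:1 concerns entrance criteria. For later trial entry, SAP 6.8 is explicit: "Patients participating in a clinical trial with a drug or device or in another international drug study or registry on the use of oral anticoagulation" are censored on entering. The A2.6 label, "Participating in any clinical trial of a drug or device", drops the qualifier that participation be current, but protocol 3.3.3 contains it, so this is editorial. What remains is retrospective reporting of A2.1, A2.4 or A2.9 as if true at enrolment. That would be a reporting fault, which the plan neither prevents nor reveals.

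**Reports need not be late.** Violations are to be acted on when identified, and protocol 3.3.4.1 requires immediate notification of discontinuations. This is correct, but it does not stop identification from following an event.

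**There is transparency.** SAP 6.2 tabulates violations on all enrolled patients. Under SAP 6.8 and 7.9.1.4, adverse-event analyses rest on enrolled, treated patients, so documented treatment-emergent events stay in the safety tables. This limits the loss to the outcome analyses. The table is not required to show treatment group, time of report or prior event.

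**Conclusion.** The concern holds on two counts. First, as written, SAP 6.2 leaves patients who fail A1.1, A1.4 or A1.5 in the eligible set when the site is silent, contrary to protocol 7.3 and although the registry holds the deciding data. Second, the SAP intends only baseline violations to count but has no safeguard against hindsight reporting of A2.1, A2.4 and A2.9, and no sensitivity analysis that would show its effect.

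The reading of the source is firm: SAP 6.2 states it and SAP 7.10.4 is consistent with it. Any resulting bias is a possibility, not a finding. Its size and direction cannot be derived from the documents, and the rate changes of up to about 10% in the working rest on assumed shares. The repair is cheap and should be made before database lock.

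**What to change.** In SAP 6.2:

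1. Derive A1.1, A1.4 and A1.5 by program for every patient from baseline CRF data (month and year of birth, diagnosis date, visit date, CHA2DS2-VASc components), in addition to End-of-Study reports. State how partial dates and missing components are treated.
2. Accept an End-of-Study violation of A2.1 to A2.9 only if it records a condition present, or an expectation documented, at or before the baseline visit. The baseline eligibility page alone would not be a sufficient source: enrolled patients will normally have passed it, so it would probably show few violations.
3. Tabulate Table 6.2:1 exclusions by treatment group, with time of report and whether an outcome event came first.
4. Add a sensitivity run of the main model that keeps patients whose exclusion was first reported after an outcome event, up to their last documented date. Name it for both studies, because SAP 7.6 limits 1160.136 to sensitivity analyses (d) and (f).

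The cost is SAP wording and a little more programming on data already collected. Some patients whom sites considered eligible will drop out on the date checks. Follow-up in the sensitivity run will be short for some patients, since documentation stops once a patient is classed as erroneously enrolled.
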